2.1 Trial design

Power@MS1 is a national, multicentre, investigator-blinded, interventional, randomised controlled, parallel group trial with multiple measurement time points. The intervention group (IG) received access to the EBBC programme, while the control group (CG) received access to an information platform based on information material from the German Multiple Sclerosis Society with optimised standard care.

2.2 Randomization

PwMS are randomized in a 1:1 ratio to either intervention or control group by block randomisation through a computer-generated system in secuTrial®. After the amendment, the therapy status was

used for stratification. All patients, that were included and randomized before the amendment, were therapy naive.

2.3 Sample Size

One event (relapse or at least one new T2 lesion) is expected in every second PwMS within 12 month in the CG. The 100 events result in a statistical power of 85% for a two-sided significance level of 5%. The assumed HR of 0.55 represents a reduction of 45% by IG compared with the CG. With a mean observation time of 12 month, the 100 events can be expected to be observed in 262 PwMS. Due to the assumption of 20% drop-outs over 1 year, it was planned to randomise 328 PwMS (164 per group).

The blinded sample size recalculation report dated on 15th September 2021 is based on a blinded data export of August 16th 2021 comprising events of 135 included patients at that time ([name] and [name], 2021). In the first definition of the primary endpoint events, only definite relapses were counted. In the second definition, possible relapses were counted, additionally. The first definition resulted in 46 primary endpoint events, while the second resulted in 51 primary endpoint events. The calculation of event rates according to the first definition and an assumed dropout rate of 20% resulted in 250 PwMS (125 per group) that have to be randomized. The calculation of event rates according to the second definition and an assumed dropout rate of 20% resulted in 216 PwMS (108 per group) that have to be randomized. The blinded sample size recalculation report resumed, that a sample size of at least 240 PwMS should be targeted.

2.4 Framework

All endpoints are tested for superiority of the intervention programme over control.

2.5 Statistical Interim Analyses and Stopping Guidance

As no significant harms are to be expected, no stopping guidelines are planned.

2.6 Timing of the Final Analysis

The final analysis will take place when all outcomes have been collected and the database is locked.

2.7 Timing of Outcome Assessments

Data is collected over a period of 12 months, with a flexible follow-up of up to 24 months in early recruited PwMS. Several measurement time points for outcome assessment are intended. They are calculated based on the randomization date: t_1 and t_0 take place before randomization; V_1 is scheduled in month 1 (30 days after randomization), V_2 in Month 3 (+90 days), V_3 in Month 6 (+180 days), V_4 in Month 12 (+365 days). For early recruited PwMS, V_5 takes place in Month 18 and V_6 in Month 24. After reaching the primary endpoint, t_x takes place. Deviations from the ideal time point are allowed to the degree of ± 28 days. Table 2 displays the assessment of variables within these time points.

Table 2 Assessments and measurement time points

| Instrument | Measurement time points | | | | | | | | |
|-------------------------------|-------------------------|----------------|----------------|----------------|----------------|----------------|-----------------------------|-----------------------------|----------------|
| | t ₋₁ | t ₀ | V ₁ | V ₂ | V ₃ | V ₄ | V ₅ [*] | V ₆ [*] | t _x |
| Demographic Data | X | | | | | | | | |
| MRI | | X | | X | X | X | X | X | |
| Clinical visit | | X | X | X | X | X | X | X | X |
| Relapse history | | X | X | X | X | X | X | X | X |
| Immunotherapy status | | X | X | X | X | X | X | X | X |
| EDSS | | X | | | | X | | | |
| RIKNO | | | | | X | | | | |
| CPS | | | | | | | X | | X |
| Decision satisfaction | | | | | | | | | X |
| Patient activation | | X | | | | X | | | |
| Emotional coping | | X | | | | X | | | |
| Changes in empowerment | | | | | | X | | | |
| Expectancy | | | X | | | | | | |
| Readiness to change | | X | | X | | X | | | |
| HAQUAMS | | X | | | | X | | | |
| EQ-5D-5L | | X | | | X | X | X | X | |
| HADS | | X | | | | X | | | |
| GLTEQ | | X | | | | X | | | |
| BSA-F | | X | | | | X | | | |
| Questionnaire of healthy diet | | X | | X | | X | | | |
| myfood24 | | X | | | | X | | | |
| Process evaluation | X | X | X | X | X | X | X | X | |
| Health economic parameters | | X | | | X | X | X | X | |

*Only in in early recruited PwMS.

3 Statistical Principles

3.1 Confidence intervals and p-values

All tests will be performed two-sided with 5% significance level. Confidence intervals (CI) will be reported with 95% confidence level.

3.2 Adherence and protocol deviations

In order to ensure patient adherence, the usage of the IG and CG programme is monitored biweekly and reacted on after 4 weeks of non-usage.

3.3 Analysis populations

The primary analysis will follow the intention-to-treat (ITT) principle. The ITT population contains all randomised patients.

The modified ITT contains all randomised patients with at least one registration in the programme. The per protocol population contains all randomised patients that used the programme regularly and reached the endpoints.

4 Trial population

4.1 Screening data

Screening data will be reported and described within a CONSORT flowchart.

4.2 Eligibility

Persons aged between 18 and 65 years with clinically isolated syndrome, suspected or confirmed MS for less than 12 months and signed informed consent, will be included. Study participants must have at least two MS-typical lesions on T2-weighted images on MRI scans and MS typical cerebrospinal fluid finding with detection of oligoclonal bands. Furthermore, access to the internet and ability to use websites is mandatory.

PwMS who are not able to provide informed consent or have a substantial psychiatric disorder or a severe cognitive deficit will be excluded. Corticosteroid therapy within 4 weeks prior to study inclusion, pregnancy and claustrophobia lead to exclusion.

4.3 Recruitment

Recruitment numbers will be summarized within a CONSORT flow diagram.

4.4 Withdrawal/follow-up

Reasons for study withdrawal will be documented using a CONSORT flowchart.

4.5 Baseline patient characteristics

All baseline patient characteristics will be summarized using descriptive statistics (e.g. mean, standard deviation, median, IQR for continuous variables and frequencies (percentages) for categorical variables) and appropriate graphical methods (e.g. boxplots, histograms, barplots) depending on the data type.

5 Analysis

5.1 Outcome definitions

A full list of outcomes and their timing is described in Section 2.7.

MRI lesion: The lesions are counted on T2-weighted MRI images. An experienced, blinded rater will evaluate MRI scans. At *baseline*, in the case that the number of lesions cannot be accurately determined, the number of lesions is set on 11 if there are more than 10 and less than 20 lesions (analog for every increment of ten). The during follow-up observed lesions are exactly counted.

Hamburg Quality of Life in MS Scale Version 10.0 (HAQUAMS) is a questionnaire for measuring quality of life in PwMS (Gold *et al.*, 2001). It consists of 44 items with mostly 5-point-likert scale. Twenty-eight of the items are subdivided into the six subscales:

- Fatigue: Items 6, 7, 8, 9
- Cognition: Items 10, 11, 12, 13
- Lower extremity: Items 17, 18, 19, 20
- Upper extremity: Items 21, 22, 23, 24, 25
- Communication: Items 29, 30, 31, 32, 33, 34
- Mood: Items 36, 37, 38, 39, 40.

Mean subscale scores are calculated, the total score is built by calculating the mean of the subscale score means: *HAQUAMS total score = mean(mean(upper extremity), mean(lower extremity), mean(fatigue), mean(cognition), mean(communication), mean(mood))*. A high total score indicates low quality of life. In case of missing data, mean substitutions are allowed for missing items.

EuroQol 5-Dimension 5-Level (EQ-5D-5L) is used to measure quality of life additionally and to calculate quality-adjusted life years (QALYs). It generates a descriptive health profile by a 5-digit code with 3125 possible health states assessing the domains mobility, self-care, usual activities, pain/discomfort, and anxiety/depression with 5-point-likert scaled responses from no problems (1) to extreme problems (5) (Herdman, 2011). This health state is transformed into index values using the German validation set. Additionally, the health on the examination day is rated on a scale ranging from 0 (worst health) to 100 (best health) (EuroQol Research Foundation, 2019).

An abbreviated 10-item version of the **Risk Knowledge in Relapsing Multiple Sclerosis V.2.0 (RIKNO)** is used to assess the risk knowledge ([name], 2017). Each item of the RIKNO is scored on a scale from 0 to 2. The total RIKNO score is calculated by summing the scores of all 10 items, ranging from 0 to 20, with higher scores indicating greater knowledge.

Control Preference Scale (CPS) is used to assess decision quality, preferred and realised role preference in decision discussion concerning immunotherapy (Degner, 1997). It consists of five response options ranging from completely passive to fully active.

Immunotherapy status is raised. If immunotherapy is started during the trial period, type, use and adherence rates will be collected during the clinical visits.

Patient Activation Measure (PAM) is used to measure the extent of patient activation (Hibbard, 2004). It consists of 13 questions and assesses the confidence and knowledge to take action in managing health and healthcare. The item scales range from 1 (Disagree at all) to 4 (Fully agree). The raw score is the sum of the items divided by the number of answered questions (excluding non-applicable items) and multiplied with 13. Afterwards the scale is transformed to a range from 0 to 100 (Moljord, 2015).

$$\text{PAM13 calculation expressed as formula: } 100 \times \frac{\left(\frac{\text{sum score}}{\text{Number of answered questions}} \times 13 \right) - 13}{(52-13)}$$

Items 1, 3 and 4 presented in Bann *et al.*, are used to measure changes in empowerment and range from 1 (disagree at all) to 4 (agree fully).

Items 10 and 24 of the **Coping Self-efficacy Scale (CSE)** are used to assess the coping capability in order to measure extent of patient activation (Chesney, 2006). The items range from 1 (Disagree at all) to 4 (agree fully).

Readiness to change is used to determine the interventions impact on willingness to change fruit and vegetable consumption resp. physical activity (Lippke, 2009). The stages are non-intenders (pre-contemplation/contemplation), intenders (preparation) and actors (action/maintenance).

Hospital Anxiety and Depression Scale (HADS) is a self-reported questionnaire and is used as a measure for depression and anxiety (Zigmond, 1983). It consists of two 7-item subscales, one for anxiety and one for depression, with a maximum score of 21 for each subscale (each item is scoring from 0 to 3), with higher scores representing higher levels of anxiety or depression. A maximum of one missing item per subscale can be estimated by the rounded mean of the six remaining items of the same subscale.

Expanded Disability Status Scale (EDSS) measures the disability in MS and is determined by the treating neurologist (Kurtzke, 1983). It ranges from 0 to 10 in half-point increments, with higher scores indicating greater disability.

Godin Leisure-Time Exercise Questionnaire (GLTEQ) is a self-reported questionnaire used to assess an individual's leisure-time physical activity levels over the previous seven days (Shephard, 1997). The *Weekly Leisure-Time Activity Score* and the *Health Contribution Score* are the sum of the product of weekly frequency and intensity of physical activity (strenuous, moderate, mild) with more than 15 minutes duration:

$$\text{Weekly Leisure-Time Activity Score} = (9 \times \text{Strenuous}) + (5 \times \text{Moderate}) + (3 \times \text{Mild}),$$

$$\text{Health Contribution Score} = (9 \times \text{Strenuous}) + (5 \times \text{Moderate}).$$

The Health Contribution Score can be classified into insufficiently active (<14), moderately active (14-23) and active (≥ 24).

Physical Activity, Exercise and Sport Questionnaire (BSA-F) is used to measure engagement in regular exercise activity within the past 4 weeks (Fuchs, 2015). BSA is a self-report questionnaire designed to assess physical activity levels in adults that includes 17 items asking about the frequency, duration, intensity and type of physical activities at work and during leisure as well as sports activity. The *total score for physical activity at work* is the sum of the received points for seated work (none = 3, rather little = 2, rather more = 1, much = 0), moderate and intense movement (none = 0, rather little = 1, rather more = 2, much = 3). The *physical activity in leisure score* is the total of the products of frequency and duration for the first seven items divided by four (unit: minutes/week). The *sports activity score* is the total of the products of frequency and duration divided by four (unit: minutes/week). The *physical activity during leisure* and *sports activity score* give the *total activity during leisure score* (only calculated both scores are available). This score can be classified into little (< 30 minutes/week), medium (30 – 120 minutes/week) and much (\geq 120 minutes/week).

Questionnaire of Healthy Diet is used to measure the frequency of intake of characteristic food groups within the last 7 days (Jannasch, 2022). The number of portion/day or week is compared with current recommendations leading to the *diet score*. This score ranges from 0 to 10, with higher scores indicating better adherence to a healthy diet.

myfood24, a 24-hour dietary recall, is used to provide nutrient intake data (Wark, 2018). In each case, it is used three times within a period of 1-3 weeks (2 weekdays, 1 weekend day).

5.2 Analysis methods

In the analysis of primary and secondary endpoints, centres with fewer than 10 patients are pooled into one centre.

The primary endpoint is analysed using a Cox proportional hazard model that includes treatment and study centre as factors. The hazard ratio (HR) will be reported with 95% CIs and p-values testing the null hypothesis of no group differences ($H_0: HR = 1$). Kaplan-Meier curves for both groups will be used to illustrate the treatment effect. The proportional hazards assumption will be checked visually by graphical diagnostics including scaled Schoenfeld residuals.

```
library(survival)

SurvObj <- Surv(FU, prim.end, data = primEndpoint)
cox.regr <- coxph(SurvObj ~ intervention + site, data = primEndpoint)
summary(cox.regr)

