# plot KM curve
plot(survfit(cox.regr))
km.by.treat <- survfit(SurvObj ~ intervention, data = primEndpoint,
                        conf.type = "log-log")
```

Secondary endpoints will be analysed using group mean comparisons between the intervention groups (δ) adjusted for baseline assessments and centre in analysis of covariance (ANCOVA) models. Least square group differences will be reported with 95% CIs and p-values testing the null hypothesis of no intervention effect ($H_0: \delta = 0$).

```

library(emmeans)

mod.sec <- lm(var ~ intervention + var_baseline + site,
               data = secEndpoints)

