# report least square group differences
tmt.means <- emmeans(mod.sec, ~ intervention)
tmt.means
pairs(tmt.means)

```

Additionally, longitudinal assessed endpoints will be analysed using Gaussian linear models for repeated measures with intervention group, time, intervention-by-time interaction and study centre as factors and baseline score as a covariate (mixed model for repeated measurements, MMRM). The error terms are assumed to follow a multivariate normal distribution with unstructured covariance matrix. Least square group differences will be reported with 95% CIs and p-values testing the null hypothesis of no intervention effect ($H_0: \delta = 0$).

```

library(lme4)
library(car)
library(emmeans)

mod.sec <- lmer(var ~ baseline_var + intervention + time + intervention * time +
                 site + (1|Patient.Id), data = secEndpoints)
summary(mod.sec)
res <- Anova(mod.sec, type = "III", test.statistic = "F")
res
tmt.means <- emmeans(mod.sec, ~ intervention * time)
pairs(tmt.means)

```

For the Readiness to Change and the Control Preference Scale, ordinal regression with logit link (proportional odds model) will be used with intervention, study centre as covariates and for readiness to change the baseline value. The model assumption will be checked.

```

library(ordinal)
library(emmeans)

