# Check model assumptions
nominal_test(mod.sec) # test partial proportional odds assumption
scale_test(mod.sec) # test for signs of scale effects

```

Data obtained through myfood24 will be used to analyse intake of selected nutrients of interest comparing mean changes in intake from baseline with post intervention between IG and CG, adjusting for baseline intake.

```

library(lme4)
library(emmeans)

mod.sec.food <- lmer(var_food ~ food_baseline + intervention + (1|Patient.Id),
                      data = secEndpoints)

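### Therapy status is a stratification factor for randomisation but is missing, without a stated reason, from the primary Cox model and every secondary model

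*SAP*

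**What the plan says.** Section 2.2 describes 1:1 block randomisation and one named stratification factor: "After the amendment, the therapy status was" the variable stratified on. It adds: "All patients, that were included and randomized before the amendment, were therapy naive". Therapy status at randomisation is therefore defined for the whole trial population.

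Section 5.2 specifies the primary analysis: "The primary endpoint is analysed using a Cox proportional hazard model that includes treatment and study centre as factors". The accompanying R code agrees, with only the intervention and site terms.

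The secondary models follow the same pattern:

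- ANCOVA: "adjusted for baseline assessments and centre in analysis of covariance (ANCOVA) models".
- Repeated measures: group, time, "intervention-by-time interaction and study centre as factors and baseline score as a covariate".
- Ordinal models: intervention and centre, plus the baseline value for readiness to change.
- myfood24: "mod.sec.food <- lmer(var_food ~ food_baseline + intervention + (1|Patient.Id", so neither centre nor therapy status.
- Lesion counts (negative binomial): baseline MRI, centre and a time offset.

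Therapy status enters the analysis only in section 5.4, in the list of subgroup and moderator variables. The SAP does not explain why it is left out of the models.

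**The concern.** Stratified randomisation balances the arms on therapy status. If that factor also predicts the outcome, the treatment comparison varies less from one randomisation to another than an analysis ignoring the factor assumes. The standard error is then too large under the null hypothesis, the test rejects less often than its nominal 5%, and power is lost. The plan adjusts for centre, which section 2.2 does not name as a stratification factor, and not for the factor that it does name.

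In a Cox model there is a second effect. The HR averaged over therapy status lies closer to 1 than the HR conditional on it, so the model without the factor estimates a slightly weaker effect. In the linear models the estimate is unbiased either way, and only precision and test size could be affected.

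At stake is some of the power claimed in section 2.3, in a trial whose target was reduced from 328 to at least 240 patients after the blinded recalculation. Validity is not threatened.

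**Working it through.** **Inputs from the SAP (section 2.3).** 100 events, HR 0.55, two-sided 5%, 85% power, 20% drop-out over one year, recalculated target of at least 240 patients.

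**The plan's own figure.** By the Schoenfeld formula, power = Φ(√events / 2 × |ln HR| − 1.96) = Φ(5 × 0.598 − 1.96) = Φ(1.03) = 84.8%. This agrees with the stated 85%. The drop-out inflation also agrees: 262 / 0.80 = 327.5, rounded up to 328.

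**Assumptions not in the SAP.** Share treated at randomisation 10% to 50%; HR of treated versus untreated patients 0.3 to 1.0; treatment HR 0.55 conditional on therapy status; therapy status binary.

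**Simulation.** N = 240, allocation balanced 1:1 within therapy strata, exponential event times, 12 months of follow-up, exponential drop-out of 20% per year, and a baseline hazard set to give 100 expected events. Cox models without and with therapy status were fitted without a centre term, with 10,000 runs per scenario under HR 0.55 and 10,000 under HR 1. The standard error of the paired power difference is 0.06 to 0.25 points.

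Power in %, without / with therapy status (loss in points):

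| Therapy HR | 10% treated | 20% | 30% | 50% |
|---|---|---|---|---|
| 0.5 | 84.2 / 84.5 (0.3) | 83.6 / 84.6 (1.0) | 82.8 / 84.4 (1.6) | 82.4 / 84.2 (1.8) |
| 0.3 | 82.7 / 83.9 (1.2) | 82.2 / 84.2 (2.0) | 80.0 / 83.4 (3.4) | 78.1 / 83.8 (5.7) |

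At a therapy HR of 0.7 the loss is 0.2 to 0.7 points. At 1.0 the difference is 0.1, no more than simulation noise.

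**Type I error.** Without the factor it runs from 5.1% (not prognostic) down to 2.9% (50% treated, therapy HR 0.3). With the factor it is 4.7% to 5.4%.

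**Estimated HR.** The mean is 0.547 to 0.579 without the factor and 0.545 to 0.550 with it.

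**Therapy started later.** Section 5.1 foresees this ("If immunotherapy is started during the trial period"). If half of the untreated patients start within the year, baseline status separates the groups less, and the losses shrink:

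| Treated at randomisation, therapy HR | No later start | Half start later |
|---|---|---|
| 20%, 0.5 | 1.0 | 0.8 |
| 30%, 0.5 | 1.6 | 1.0 |
| 30%, 0.3 | 3.4 | 2.5 |
| 50%, 0.3 | 5.7 | 3.9 |

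**Sensitivity to the set-up.** A separate simulation used the SAP's 50% control event rate at 12 months, blocks of four, and 25% or 50% treated. The power loss without the factor, in points, was:

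| Therapy HR | N = 328 | N = 240 |
|---|---|---|
| 0.6 | 0.4–0.8 | 0.5–1.0 |
| 0.4 | 1.1–2.4 | 1.5–3.8 |
| 0.25 | 1.6–4.9 | 3.8–8.5 |

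Type I error at N = 328 without the factor was 4.0–4.2% at therapy HR 0.4 and 2.7–3.3% at 0.25. With it, the figures were 4.8–4.9% and 4.6–4.9%. At N = 240 this set-up yields only about 89 to 91 events, so absolute power is lower (about 79–81% with the factor). The differences are the relevant figures.

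A log-rank test compared with one stratified by therapy status (N = 240, 100 expected events) points the same way. The losses are about 0.1–0.5 points at therapy HR 0.7, 0.7–1.6 at 0.5 and 2–5 at 0.3, with type I error down to about 3.4% without stratification.

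**Linear models.** If r is the partial correlation of therapy status with the score, type I error without the factor is 2 × (1 − Φ(1.96 / √(1 − r²))). For assumed r = 0.1, 0.2 and 0.3 this gives 4.9%, 4.5% and 4.0%, with no bias.

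**The case against.** The other side accepts the textual facts and disputes their weight. Its strongest points are these.

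- **Nothing becomes invalid.** The HR averaged over therapy status is a legitimate target, and section 2.3 does not say whether 0.55 is averaged or conditional. If it is averaged, the loss is a gain not taken and not a shortfall against 85%. This stands, and it is why the point is a recommendation.
- **The loss is small unless assumptions are stacked.** At therapy HR 0.5 or weaker it stays below 2 points. Treated patients can come only from the post-amendment part of the trial, so a 50% overall share would need a heavily treated later cohort, which the SAP does not describe. Treatment started later dilutes the effect further. This also stands.
- **The simulated model is not exactly the planned one.** Centre was omitted and could absorb part of the effect if treatment practice differs between centres. Follow-up was fixed at 12 months although early recruits may have up to 24. Both limit the precision of the figures but not their direction.
- **The case is weaker for the secondary models.** Nothing in the SAP shows that therapy status predicts questionnaire or diet scores once the baseline value is in the model, and no figures were produced for the ordinal and negative binomial models. There the argument is mainly consistency with the randomisation.
- **Therapy status is examined in section 5.4.** A subgroup analysis does not change the standard error or size of the primary test, so this does not answer the point.

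**Conclusion.** The concern holds. The only stratification factor named in section 2.2 is absent from every model in section 5.2, with no reason given. The consequence is a conservative primary test and some lost power, provided therapy status is prognostic. It is neither an inflated error rate nor bias in the linear models.

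In the scenarios with 240 patients and 100 expected events, the loss is below 2 points for a therapy HR of 0.5 or weaker. It reaches 3.4 points at 30% treated and 5.7 at 50% treated when the therapy HR is 0.3, and it vanishes if therapy status does not matter. The lower-event set-up at N = 240 reaches 8.5 points, but only with a therapy HR of 0.25 and half the patients treated. All of these sizes depend on a treated share and a prognostic effect that the SAP does not give.

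This should be changed because the correction costs almost nothing and the benefit is never materially negative. The expected damage from leaving it is modest.

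**What to change.** Before unblinding, add therapy status at randomisation to the primary model, coding all pre-amendment patients as untreated: `coxph(Surv(FU, prim.end) ~ intervention + site + therapy_status)`, or use `strata(therapy_status)` in place of the covariate. State the levels of the factor, since section 2.2 does not define them. Add the same term to the ANCOVA, repeated-measures, ordinal, myfood24 and negative binomial models so that the analysis matches the randomisation. If the factor is left out on purpose, one sentence giving the reason is enough.

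The cost is a line of SAP text and, for a two-level factor entered as a covariate, one degree of freedom per model. No new data are needed: the value was used to randomise post-amendment patients and is known for all earlier ones. Fixing the choice now also avoids a later choice between adjusted and unadjusted primary results.

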# report least square group differences
tmt.means <- emmeans(mod.sec.food, ~ intervention)
pairs(tmt.means)

```

MRI lesion counts will be analysed using a negative binomial regression model adjusted for baseline MRI and centre and time to last observed lesion as offset. If observations are censored, the model would be adapted accordingly.

```

library(MASS)

mod.les <- glm.nb(lesions_fu ~ lesions_baseline + intervention + site +
                   offset(log(time_lastObs)), data = secEndpoints)
summary(mod.les)
tmt.means <- emmeans(mod.les, ~ intervention)
pairs(tmt.means)

```

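### The primary Cox model omits the baseline T2 lesion count and so forgoes power to the extent that the count is prognostic

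*SAP*

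**What the plan says.** Section 5.2 of the SAP defines the primary analysis: "The primary endpoint is analysed using a Cox proportional hazard model that includes treatment and study centre as factors". The code agrees with the text, as its model call reads "cox.regr <- coxph(SurvObj ~ intervention + site, data = primEndpoint" and then closes. Neither has a baseline lesion term.

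The baseline count is nevertheless available:

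- **Timing.** Table 2 in section 2.7 marks an MRI at t0, and that section places t0 before randomisation.
- **Coding.** Section 5.1 gives a rule for the baseline count. It is exact where possible; otherwise it is set by bands of ten, with 11 standing for the band above 10 and below 20.
- **Range.** Section 4.2 requires at least two lesions for entry.
- **Use elsewhere.** Later in section 5.2: "MRI lesion counts will be analysed using a negative binomial regression model adjusted for baseline MRI and centre". Section 5.4 also lists number of lesions among the subgroup and moderator variables.

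Section 1.3 makes a new T2 lesion one of the two ways of reaching the primary endpoint. The SAP gives no reason for leaving the baseline count out of the primary model, and no estimate of how strongly it predicts the endpoint.

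**The concern.** The SAP adjusts the follow-up lesion count for the baseline lesion count, but not the primary endpoint, of which new lesions are a part. Power matters most for the primary test.

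In a Cox model, leaving out a covariate that predicts the outcome moves the estimated treatment HR towards 1, relative to the HR conditional on that covariate. It also leaves any chance imbalance in the covariate uncorrected. The type I error is not affected. What may be lost is power that could be had from data already collected.

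**Working it through.** **1. The plan's own figure.** Inputs from section 2.3: 100 events, HR 0.55 ("The assumed HR of 0.55 represents a reduction of 45% by IG compared with the CG"), two-sided 5%. Allocation is 1:1 (section 2.2). By Schoenfeld's formula, power = Φ(√d · |ln HR| / 2 − 1.960).

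- |ln 0.55| = 0.598, and √100 · 0.598 / 2 = 2.989.
- 2.989 − 1.960 = 1.029, and Φ(1.029) = 84.8%.

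This matches the stated 85%. No covariate enters the calculation.

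**2. Trial size for the simulation.** Section 2.3 gives the control risk: "One event (relapse or at least one new T2 lesion) is expected in every second PwMS within 12 month in the CG". With exponential times, the 12-month risk in the intervention group is 1 − 0.5^0.55 = 0.317. The mean risk is (0.500 + 0.317) / 2 = 0.4085, so 100 events need 100 / 0.4085 ≈ 245 patients. The simulation used 244 (122 per arm).

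**3. Simulation assumptions.** None of these is given in the SAP except the control risk.

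- Exponential event times, 12 months' follow-up, no dropout and no centre effect.
- Log baseline count normal, with median count 10, SD 0.8 on the log scale and a minimum of 2. Every count above 10 is banded by tens, so the covariate is analysed in its coarser form.
- Event HR per SD of log count of 1.00, 1.22, 1.49, 1.82 or 2.23.
- 6,000 trials per setting. The Monte Carlo standard error of each power is about √(0.84 · 0.16 / 6000) = 0.5 points.

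**4. Results.** Section 2.3 does not say whether HR 0.55 is the effect conditional on lesion load or the marginal (unadjusted) effect, so both were run.

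Reading A: 0.55 is the conditional HR.

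| HR per SD | Unadjusted HR | Power without count | Power with count | Gain (points) |
|---|---|---|---|---|
| 1.00 | 0.546 | 84.1% | 84.1% | 0.0 |
| 1.22 | 0.550 | 83.3% | 83.9% | 0.6 |
| 1.49 | 0.560 | 81.6% | 84.3% | 2.7 |
| 1.82 | 0.577 | 77.6% | 83.3% | 5.7 |
| 2.23 | 0.598 | 73.1% | 85.0% | 11.9 |

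Reading B: 0.55 is the marginal HR. The conditional HR was set to 0.546, 0.535, 0.518 and 0.497 in turn, which gave unadjusted HRs of 0.543 to 0.546.

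| HR per SD | Power without count | Power with count | Gain (points) |
|---|---|---|---|
| 1.22 | 84.0% | 84.3% | 0.3 |
| 1.49 | 84.2% | 86.5% | 2.3 |
| 1.82 | 84.9% | 89.5% | 4.6 |
| 2.23 | 85.7% | 93.6% | 7.9 |

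Across both readings the gain is about 0 to 1, 2 to 3, 5 to 6 and 8 to 12 points at the four strengths above 1.00. Adding the covariate did not lower power in any setting. The gains at 1.22 are too small to distinguish firmly from nil.

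**The case against.** The SAP contains no error here. Text and code agree, the power figure reproduces, and a Cox model with arm and centre is valid in a randomised trial. Chance imbalance is already reflected in the confidence interval and p-value. Which covariates to add is a design judgement. All of this stands, and the point is therefore one of efficiency.

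The internal evidence that the count is prognostic is also limited. Adjusting a lesion count for its baseline value does not show that the baseline count predicts a composite that includes relapse. The list in section 5.4 concerns effect modification, not prognosis. The ANCOVA models adjust for the baseline value of the same scale, and a time to first event has no such value. So the size of the gain cannot be taken from the SAP.

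A reader might infer that the primary test falls short of the stated 85%. The SAP does not support that. The shortfall appears only under reading A, and section 2.3 does not describe 0.55 as conditional on lesion count. Under reading B the unadjusted test keeps 84.0% to 85.7%, and adjustment only adds to it.

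Adjustment has some cost: a functional form must be chosen for a partly banded variable, and missing baseline counts would bring imputation into the primary test. Both costs are minor for a single term against about 100 events.

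**Conclusion.** The point holds as a conditional one. The primary model leaves out a pre-randomisation value that is already collected, closely related to one endpoint component and already used in the SAP's own lesion-count model. If that value is prognostic for time to first new lesion or relapse, power is forgone: from under 1 point for weak prognosis to about 12 points at the top of the assumed range. If it is not, nothing is lost.

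The omission and the direction of its effect are certain given prognosis; the size is not. It rests on an assumed HR per SD of 1.22 to 2.23 and on the simplified simulation. An unconditional statement that the test loses power, or that the analysis is biased, would go further than the SAP allows. The change is worth making because the possible gain is useful and the cost is small.

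**What to change.** Before unblinding, specify the primary model in section 5.2, in text and code, as `coxph(Surv(FU, prim.end) ~ intervention + site + log(lesions_baseline), data = primEndpoint)`, with the baseline count coded as in section 5.1. The log is defined because section 4.2 requires at least two lesions.

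State that the reported HR is conditional on lesion load, and keep the treatment-plus-centre model as a sensitivity analysis. State also that a missing baseline count is handled by the multiple imputation in section 5.3. By default `coxph` drops such patients, which would conflict with the intention-to-treat population.

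The cost is one model term and one degree of freedom, with no new data. The interpretation of the HR changes slightly, and the primary result relies on the planned imputation wherever a baseline count is missing. If the sponsor prefers the present model, a sentence giving the reason would settle the point.
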